6.6.2.2 Treatment-emergent AEs

Treatment-emergent AEs (TEAEs) are defined as any AE that occurs or worsens after the first dose of the treatment in TP1. All AEs occurring after the first dose and until the end of the study participation are considered treatment-emergent events, including the adverse events occurring during the washout period in between the two treatment periods. Adverse events occurring during the Safety Follow-up period are considered TEAEs if they occur within 14 days of the start of the Safety Follow-up Period.

6.6.2.3 Adverse Events of Special Interest (AESI)

The AESIs for all study drugs (MLS-101 and placebo) include the following:

- Modification of study drug dose due to hyperkalemia (e.g., dose reduction, dose hold, or permanent dose discontinuation)
- Modification of study drug dose due to hyponatremia (e.g., dose reduction, dose hold, or permanent dose discontinuation)
- Hypotension with symptoms (e.g., light-headedness, dizziness, presyncope, or syncope)
- Severely elevated blood pressure (AOBP SBP >180 mmHg or DBP >110 mmHg)
- Modification of study drug dose due to hypercortisolism (serum cortisol >35 µg/dL, confirmed by 24-hour urinary free cortisol)
- Discontinuation of study drug due to hypocortisolism confirmed by ACTH (Cosyntropin) stimulation test
- Overdose of study drug
- Modification of study drug dose due to reduction in kidney function (e.g., dose reduction, temporary or permanent hold on dosing)

Note: AESIs are reported on the eCRF.

6.6.2.4 Missing or Partial Dates for AEs

Imputation rules for the missing or partially missing AE dates are as follows.

Completely missing Start Date rules in order of application:

- Rule #1. Start date will be imputed as occurring on the first date of the study investigational drug administration, except if complete or partial end date is prior to the study investigational drug administration date.
- Rule # 2. If rule #1 does not apply, then the AE Start Date will be imputed as occurring on the date of the ICF.

Note: If the complete or partial study AE End Date is before the date of the ICF, then the event is not an AE.

Partially missing AE Start Date -missing MONTH and DAY rules in order of application:

- Rule #1. AE Start Day and Month will be imputed as January 1, except if AE Start Year is the same, or earlier, than the year of the first administration of the study investigational drug.
- Rule #2 If rule #1 does not apply, then AE Start date will be imputed as occurring on the first date of the study investigational drug administration, except if AE Start Year is prior to Year of the first study investigational drug administration or complete or partial end date is prior to the study investigational drug first administration date.

- Rule #3. If rules #1 and #2 do not apply, AE Start date will be imputed as occurring on the date of the ICF.

Note: If the complete or partial study AE End Date is before the date of the ICF, or the Month and Year of the AE start Date is prior than Month and Year of the ICF, then the event is not an AE.

Partially missing AE Start Date – missing DAY rules in order of application:

- Rule #1. AE Start Day will be imputed as “1”, except if AE Start Month and Year are the same as the Month and Year of the first administration of the study investigational drug or, as the Month and Year of the ICF.
- Rule #2 If rule #1 does not apply, and the AE Start Month and Year are the same as Month and Year of the first study investigational drug administration, then the date will be imputed as the date of the first study investigational drug administration, except if complete end date is prior to the study investigational drug first administration date, in which case the start Day will be imputed as 1.
- Rule #3. If rules #1 and #2 do not apply, Start date will be imputed as occurring on the date of the ICF.

Partial or missing AE resolution dates will not be imputed.

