6.6 Safety Evaluations

6.6.1 Safety Treatments Displays

Safety analyses will be conducted using the Safety Analysis Set. All safety events starting or worsening of the existing AE between the first dose in the TP1 and the First dose in the TP2 (Week 0 to Week 8, including the washout) will be allocated to the medication received first in the randomized sequence (lorundrostat or placebo). All AEs starting or worsening of the existing AE from the first dose in the Treatment Period 2 to the End of Treatment / End of Study, whichever is later, will be allocated to the medication starting in the TP2 (lorundrostat or placebo).

All AE Summary displays will present AEs by Treatment Period and Treatment Group within the period and, by Treatment Group Total.

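### No AE start-date imputation rule uses the first TP2 dose, so some incompletely dated TP2 events in both sequences are charged to the first-period drug

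*SAP*

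**What the plan says.** **Attribution (SAP 6.6.1).** The first drug in the sequence is charged with "All safety events starting or worsening of the existing AE between the first dose in the TP1 and the First dose in the TP2", washout included. The second drug is charged with events "from the first dose in the Treatment Period 2" up to the end of treatment or end of study, whichever is later. AE displays are by period, by treatment within period, and by treatment in total.

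**Imputation of start dates (SAP 6.6.2.4).**

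- *Completely missing:* "Start date will be imputed as occurring on the first date of the study investigational drug administration", unless the event ended before that dose. For that exception: "If rule #1 does not apply, then the AE Start Date will be imputed as occurring on the date of the ICF".
- *Month and day missing:* "AE Start Day and Month will be imputed as January 1, except if AE Start Year is the same, or earlier"; the comparison is with the first-dose year. If the year is the same, the first-dose date is used.
- *Day missing:* day 1 of the known month, "except if AE Start Month and Year are the same as the Month and Year of the first administration of the study investigational drug"; the consent month is excepted too.
- *End dates:* "Partial or missing AE resolution dates will not be imputed". A recorded end date is compared only with the first dose or with consent, never with the first TP2 dose.

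The first TP2 dose is a separately derived date in SAP 5.2, but no rule in 6.6.2.4 refers to it.

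**The concern.** The imputation rules are those of a parallel-group trial, where the one question is whether an event began before or after first exposure. That is enough to decide treatment-emergent status in SAP 6.6.2.2. In a 2x2 crossover the start date also decides which drug the event counts against, and the dividing date for that is the first TP2 dose. A rule that ignores this date can put an event in the wrong period and so under the wrong drug.

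At stake is the lorundrostat–placebo comparison in every AE table of SAP 6.6.2.6, including events leading to discontinuation or dose modification. With about 60 subjects, a few reallocated events can change a comparison at preferred-term level. The listings in 6.6.2.6 make no provision for marking imputed dates, so a reader could not see that it had happened.

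**Working it through.** The plan gives no figure to reproduce. The check applies the 6.6.2.4 rules to true TP2 onsets and then attributes each event by 6.6.1.

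**Inputs.** From SAP 2.1: TP2 runs from Week 8 to Week 12, so the planned first TP2 dose is 56 days after the first TP1 dose; allocation is 1:1 to LP and PL. Assumed: consent 28 days before the first dose; onset uniform over weeks 8–12 (28 days) or, to include follow-up, weeks 8–14 (42 days). The rules were applied to 730 consecutive TP1 first-dose dates, giving 730 × 28 = 20,440 and 730 × 42 = 30,660 onsets. An onset is misallocated if its imputed date falls before the first TP2 dose.

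**Share of true TP2 onsets charged to the first-period drug.**

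| Missing part | Weeks 8–12 | Weeks 8–14 |
|---|---|---|
| Whole date | 100% | 100% |
| Month and day | (16,576 + 3,052) / 20,440 = 96% | (24,276 + 4,578) / 30,660 = 94% |
| Day only | 10,696 / 20,440 = 52% | 10,746 / 30,660 = 35% |

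For year-only dates the share is 100% when onset is in the same year as the first TP1 dose. When onset is in a later year it is 3,052 / 3,864 = 79% (weeks 8–12) or 4,578 / 6,384 = 72% (weeks 8–14).

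For day-missing dates every error lies in the calendar month of the first TP2 dose: 10,696 / 11,368 = 94% of onsets in that month (weeks 8–12), and none of the 9,072 onsets in later months. No TP2 onset fell in the month of the first TP1 dose, so these errors come from the day-1 rule and not from the first-dose anchor.

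**Hand check of the day-missing figure.** Take a 30-day month with the TP2 start day s uniform on 1 to 30. If s = 1, imputation to day 1 is harmless. For s = 2 to 30 the misallocated days are min(28, 31 − s), which sum to 28 + (28 + 27 + … + 1) = 28 + 406 = 434. Then 434 / 30 = 14.5 days and 14.5 / 28 = 52%. Over 42 days the sum is 29 + 28 + … + 1 = 435, and 435 / 30 / 42 = 35%.

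**Example.** A PL subject has a first TP1 dose on 10 Sep 2024 and a first TP2 dose on 5 Nov 2024.

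| What is recorded | Imputed start | Charged to |
|---|---|---|
| Nothing (true onset late Nov) | 10 Sep 2024 | placebo |
| 2024 | 10 Sep 2024 | placebo |
| Nov 2024 | 1 Nov 2024 | placebo |
| Dec 2024 (true onset in Dec) | 1 Dec 2024 | lorundrostat (correct) |

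**Direction.** For any onset after the first TP1 dose, each rule gives a date on or before the true onset. Events can therefore move from TP2 to TP1, but TP1 and washout events cannot move into TP2. By drug, the shift is lorundrostat to placebo in PL and placebo to lorundrostat in LP.

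**Net effect (illustrative, assumed counts).** Let each period have a = 10 events on lorundrostat and b = 5 on placebo, with a fraction f = 10% of TP2 dates completely missing.

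- Lorundrostat: a + a(1 − f) + bf = 10 + 9 + 0.5 = 19.5 (true 20)
- Placebo: b + b(1 − f) + af = 5 + 4.5 + 1 = 10.5 (true 10)

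The difference falls from 10 to 9. In general it shrinks by 2f(a − b), so the two sequences do not cancel unless a = b. With f = 1% the counts are 19.95 and 10.05.

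**The case against.** **Few dates will be missing.** AEs are collected at every visit, 2 to 4 weeks apart in the treatment and washout periods. The eCRF has edit checks and queries for completeness (Protocol 10.9). SAEs and AESIs must be reported within 24 hours (Protocol 8.4.1 and 8.4.7), so the most important events are the least likely to lack a month. The outlier tables and the potassium adjudication (SAP 6.6.3.4 and 6.6.3.5) rest on laboratory values and not on AE start dates. All of this stands, and it limits the size of the problem.

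**The first administration might mean the first dose of each period.** The text does not support this. SAP 5.2 defines the TP1 and TP2 first doses as separate items, 6.6.2.4 has no period qualifier, and SAP 6.6.6 ties similar wording to the dose after randomization. If a period-specific meaning is intended, the SAP needs to say so.

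**Defaulting ambiguous events to lorundrostat can be worse than the present rule.** This also stands. Keep the 10 and 5 events per period, with 10% of dates completely missing in both periods. The present rule gives 19.5 vs 10.5, a difference of 9. In LP the default leaves 0.5 placebo events on lorundrostat; in PL it moves 0.5 first-period placebo events to lorundrostat. The result is 21 vs 9, a difference of 12. If end dates identify all the TP1 events, PL is correct and the result is 20.5 vs 9.5, a difference of 11. The truth is 10, so the error changes from −1 to +2 or +1. Such a default is a conservative convention and not a correction.

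**Stronger readings a reader might infer.** One is that every incompletely dated TP2 event is pulled back to the first TP1 dose. The rules also use 1 January, day 1 of the month and the consent date, and a day-missing event in a month after the TP2 start month is placed correctly. Another is that only lorundrostat events are lost. With both sequences randomized, placebo events in LP move to lorundrostat as well.

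**Conclusion.** The point holds as a minor defect. A stated rule gives the wrong drug attribution for some incompletely dated TP2 events in both sequences, because the date that decides attribution in 6.6.1 is absent from 6.6.2.4. The percentages in the table assume a first TP2 dose at day 56 and uniform onset. The day-missing figure depends most on how much follow-up is counted as TP2.

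These are shares of incompletely dated TP2 events, not of all AEs. The documents give no count of such dates. The effect on the tables is therefore unknown and probably small, and they do not support a claim that a safety signal would be hidden. The dilution is conditional on lorundrostat causing more AEs than placebo. Treatment-emergent status is not affected, since every imputed date for a TP2 onset is on or after the first TP1 dose.

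**What to change.** Add a TP2 anchor to SAP 6.6.2.4, applied in this order:

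1. Use the known month and year, and any complete or partial end date, to decide whether onset on or after the first TP2 dose is impossible, possible or certain. An event that ended before the first TP2 dose stays in TP1. An event known to start in a month after the TP2 start month stays in TP2, as now. Impute within the period so determined.
2. For events still compatible with both periods, including day-missing events in the TP2 start month, pre-specify one convention. Attribution to lorundrostat is an option; it would match SAP 6.6.2.5, which treats missing relatedness as related. It should be labelled as conservative.
3. Show the AE counts under the alternative attribution as well.
4. Flag and list every AE with an imputed start date.

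The cost is one rule, one flag and one extra tabulation; the first TP2 dose date is already derived in SAP 5.2. The downside is that a conservative convention may charge a few placebo or washout events to lorundrostat and overstate the difference. The alternative tabulation makes that visible.

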6.6.2.5 AE Relatedness

CRFs have assessment of relatedness to investigational drug (lorundrostat/placebo) and SGLT2i or placebo. Only relatedness to lorundrostat will be used for the determination of relatedness. AEs marked as “Possibly” or “Definitely” related to investigational study treatment (lorundrostat or placebo) will be classified as being related to the study investigational drug (“related”). All other AEs will be classified as not related to investigational study drug. If the relationship to the investigational study treatment (lorundrostat or placebo) is missing, the event will be assigned as related to the study investigational drug.

6.6.2.6 AE Displays

An overall AE summary will be presented by the number and percent of subjects with one or more events of specific type and total number of events of specific type by Treatment Period, Treatment Group within Treatment Period and Treatment Group in Total with the following:

- TEAEs
- TEAEs by worst severity (mild/moderate/severe)
- Treatment-related TEAEs
- Treatment-related TEAEs by worst severity (mild/moderate/severe)
- Serious AEs (SAEs)

- Treatment Emergent SAEs
- Treatment-related Treatment-emergent SAEs
- Adverse Events of Special Interest (AESIs)
- TEAEs leading to permanent discontinuation of study investigational drug
- TEAEs leading to dose modification of the investigational drug
- AEs with death as an outcome
- TEAEs with death as an outcome
- Treatment-related AEs with death as an outcome

The following AE summaries will be produced by MedDRA SOC and PT with the counts and percent of subjects with one or more event and counts of events for each PT and SOC level. The outputs will be presented by the alphabetic order of SOC and PT classes. The summary will be by Treatment Period, Treatment Group within Treatment Period and Treatment Group in Total.

- Any AE
- AEs in Run-In Period
- TEAEs
- TEAEs by worst severity (mild/moderate/severe)
- Treatment-related TEAEs
- Treatment-related TEAEs by worst severity (mild/moderate/severe)
- Serious AEs (SAEs)
- Treatment Emergent SAEs
- Treatment-related Treatment -emergent SAEs
- Adverse Events of Special Interest (AESIs)
- TEAEs leading to permanent discontinuation of study investigational drug
- TEAEs leading to dose modification of the investigational drug
- AEs with death as an outcome
- TEAEs with death as an outcome

The following AE listings will be prepared:

- AEs in Run-In Period
- TEAEs
- TEAEs by worst severity (mild/moderate/severe)

- Treatment-related TEAEs
- Treatment-related TEAEs by worst severity (mild/moderate/severe)
- Serious AEs (SAEs)
- Treatment Emergent SAEs
- Treatment-related Treatment -emergent SAEs
- Adverse Events of Special Interest (AESIs)
- TEAEs leading to permanent discontinuation of study investigational drug
- TEAEs leading to dose modification of the investigational drug
- AEs with death as an outcome
- TEAEs with death as an outcome

6.6.3 Laboratory Data

6.6.3.1 Reference Range for local serum potassium

The reference range for the local laboratory serum potassium for reporting will be established as follows:

ANRLO = [REDACTED]; ANRLHI = [REDACTED]. The reference ranges need to be derived according to these reference ranges.

6.6.3.2 General summaries of laboratory data

Laboratory test results (including hematology, serum chemistry, spot urine, urinalysis, 24-hour urine, and ACTH) and abnormal laboratory values will be presented in data listings. Summaries of observed values and changes from baseline will be presented by the Treatment Period and Treatment Group within the period and by Treatment Group in Total for each analysis visit. The SI units will be presented. In addition, the conventional units will be presented for the following tests.

Table 8 Laboratory tests to be presented in conventional units

Laboratory Test Name	Specimen
C Reactive Protein	Serum
Cortisol, ACTH Stimulation, 30 Minute	Serum
Cortisol, ACTH Stimulation, 60 Minute	Serum
Cortisol, ACTH Stimulation, Baseline	Serum
Cortisol, Morning Collection	Serum
Creatinine	Serum
Direct Bilirubin	Serum

Glucose	Serum
Glucose, Random	Serum
Total Bilirubin	Serum
Creatinine	Urine

Note: all laboratory tests will be presented in SI units. The tests presented in this table will also be presented using conventional units.

Shifts from baseline to post-baseline values in abnormality status according to normal range criteria will be provided for applicable lab parameters.

6.6.3.3 Additional summaries

The following laboratory tests will be in addition summarized using geometric mean, geometric standard error and two-sided 90% geometric confidence intervals. Only the analysis value will be summarized, by Treatment Period and Treatment Group within the period and by Treatment Group in Total for each analysis visit.

Table 9 Laboratory tests summarized by geometric means

Laboratory Test Name
Urine Albumin Excretion Rate
Serum Aldosterone
Serum Aldosterone / Renin Ratio
Urine Aldosterone Excretion Rate
Plasma Renin Activity
24-h Urine Aldosterone to Creatinine Ratio
Urine Albumin to Creatinine Ratio (both spot urine and 24-h urine)
Urine Protein Excretion Rate
Urine Albumin
Urine Protein to Creatinine Ratio (both spot and 24-h urine)
Urine Protein

6.6.3.4 Outlier Analysis

The following outlier analysis will be created by Treatment Period and Treatment Group within the period and by Treatment Group in Total.

Table 10 Patients with one or more chemistry analyte values with elevated or low values meeting specified levels for the following parameters

Parameter	Categories
Sodium (low) mEq/L	Level 1
	Level 2
	Level 3

Potassium (high) mEq/L	Level 1 [REDACTED] Level 2 [REDACTED] Level 3 [REDACTED]
---------------------------	--

Table 11 Patients with one or more kidney function analyte values exceeding specified levels

Parameter	Categories
Creatinine, high (mg/dL)	Level 1 [REDACTED] x baseline) Level 2 [REDACTED] x baseline) Level 3 [REDACTED] x baseline)
eGFR 2021 (low) mL/min/1.73 m ²	Level 1 ([REDACTED] decrease) Level 2 ([REDACTED] decrease) Level 3 ([REDACTED] decrease)
eGFR 2012 (low) mL/min/1.73 m ²	Level 1 [REDACTED] decrease) Level 2 [REDACTED] decrease) Level 3 (≥75% decrease)

6.6.3.5 Adjudication of outlier analysis

The Adjudication Committee will review the outlier laboratory data based on the locked and unblinded subjects who experienced at least 1 elevated potassium post-randomization, irrespective of period. The committee will review each subject and their associated event(s) assignment and provide documented rationale in the revised listing. Details of the adjudication procedure will be specified in the charter. The adjudicated listing will be used to create adjusted outlier tables using the same layout as in the previous section.

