2.3.1.1. Risk of Hyperkalemia

Increased potassium levels have been observed in non-clinical studies of lorundrostat and are a known risk of MRAs, in general. Early healthy volunteer studies with lorundrostat revealed a trend of mild increase in serum potassium, although none of these increases were assessed as clinically significant. In a Phase 2 study in [REDACTED] subjects with uncontrolled hypertension (MLS-101-201), hyperkalemic events were the most frequently reported AEs. Adjusting the event rate to censor values that failed quality control criteria designed to rule out non-reproducible and factitious hyperkalemia (e.g., elevated lactate dehydrogenase (LDH), with the failure to reproduce in a second blood sample drawn as soon as possible while the subject was on the same dose of lorundrostat), the number of events and subjects, presented as n events (N individuals) deemed as mild, moderate and severe laboratory abnormalities were: [REDACTED] respectively. In all cases, an electrocardiogram (ECG) was obtained and in no case were clinically significant abnormalities identified.

In this study, to mitigate potential risks associated with hyperkalemia, subjects will be required to have a serum potassium of [REDACTED] prior to starting investigational drug and return to the clinic regularly to assess potassium levels locally at each in-clinic visit following initiation of treatment with lorundrostat. Clinical monitoring will allow early detection of potential AEs or trends that may be concerning, particularly those associated with increasing potassium levels.

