Treatment-emergent SAEs were reported in three subjects, one of which was deemed to be possibly related to lorundrostat in a subject with worsening of pre-existing hyponatremia, which reversed after treatment discontinuation. The two active QD doses saw modest increases in potassium levels across the cohorts of 0.25 mmol/L with the 50 mg QD and 0.29 mmol/L with the 100 mg QD dose. Six subjects experienced transient elevated serum potassium greater than 6.0 mmol/L, none of which were considered an SAE, and all rapidly resolved after discontinuation or dose adjustment, which is consistent with the short half-life of lorundrostat. One of the events was assessed as erroneous due to sample misprocessing. As anticipated, and in a manner similar to ACEi and ARB, the BP lowering effect of lorundrostat led to a beneficial, reversible dose-dependent reduction in eGFR. Finally, the selectivity of lorundrostat for aldosterone inhibition was confirmed as cortisol levels were not observed to be inhibited across the range of doses. There were no notable findings in terms of vital signs, physical examination, or ECG parameters.

This study may also provide commercially available dapagliflozin 10mg QD for subjects naïve to SGLT2i or who elect to take study provided dapagliflozin in lieu of their regularly prescribed SGLT2i. Dapagliflozin 10 mg has been chosen because it is the dose that is Food and Drug Administration (FDA)-approved to reduce the risk of sustained eGFR decline, end stage kidney disease, cardiovascular death, and hospitalization for heart failure in adults with CKD at risk of progression in patients with $eGFR \geq 25$ mL/min/1.73 m². This dose has also been demonstrated to reduce albuminuria in diabetic and non-diabetic patients with CKD in the DAPA-CKD trial (Jongs [2021](#)).

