2.5 Blinding

The identity of study drug assignments (lorundrostat or placebo) during the DB treatment periods will be concealed from the Investigator, the subject, research center staff, and all personnel involved in the conduct of the study, with the exception of the unblinded Sponsor drug management staff who will oversee the study drug allocations and RTSM/dispensing compliance at the study centers.

Except when it is essential for the medical management of the subject, unblinding the treatment assignment will be considered a protocol deviation. If possible, the Investigator should contact the Sponsor before unblinding any subject's treatment assignment. If this is not possible, the Sponsor should be notified within 24 hours after the unblinding event. Emergency treatment allocation information will be available by secured access to the RTSM system. After unblinding, the subject will be discontinued from study drug treatment, but will continue participation in the study, including participation in all remaining visits and assessments, until the EoS visit. The reason for unblinding must be documented in the electronic case report form (eCRF).

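### Potassium outliers are adjudicated on unblinded data with no stated masking or criteria, which leaves the adjusted by-treatment outlier tables open to bias

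*SAP*

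**What the plan says.** SAP 6.6.3.4 plans counts of subjects with low sodium, high potassium, raised creatinine or reduced eGFR: "The following outlier analysis will be created by Treatment Period and Treatment Group within the period and by Treatment Group in Total".

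SAP 6.6.3.5 adds a second step. The Adjudication Committee "will review the outlier laboratory data based on the locked and unblinded subjects who experienced at least 1 elevated potassium post-randomization", whichever period the value fell in. Its task is given in one sentence: "The committee will review each subject and their associated event(s) assignment and provide documented rationale in the revised listing". The result is then used: "The adjudicated listing will be used to create adjusted outlier tables using the same layout as in the previous section". On method, the SAP says only this: "Details of the adjudication procedure will be specified in the charter".

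Blinding is covered in SAP 2.5: "The identity of study drug assignments (lorundrostat or placebo) during the DB treatment periods will be concealed from the Investigator", and also from subjects, site staff and others running the study. That statement is limited to the double-blind periods and does not mention the committee. The SAP version history shows that the adjudication step came in with version 2.0.

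**The concern.** Whether a high potassium should stand in an outlier table is a judgement. The SAP places that judgement after lock, on unblinded data, without saying that adjudicators are kept from the treatment codes and without stating what would justify a change. An adjudicator who knows the treatment may, without intending to, ask more of a value on one treatment than on the other.

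The selection is one-sided. A subject enters review only after an elevated value, so review can take a subject out of the adjusted table, or perhaps change the level recorded, but cannot bring in a subject who was not already counted.

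Raised potassium is a leading safety question for this drug. Protocol 2.3.1.1 reports hyperkalaemia as the most frequent adverse event in the Phase 2 hypertension study. If more elevations fall on lorundrostat, more of the records open to removal are there too. What is at stake is whether the drug-placebo contrast in the adjusted tables can be read at face value.

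**Working it through.** **No stated figure to reproduce.** The point depends on no power, alpha or event count given in the plan. It is checked by comparing the text, then by a count illustration.

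**Text, side by side**

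1. *Masking.* The only reference to treatment knowledge in SAP 6.6.3.5 is that the data are unblinded. SAP 2.5 does not extend to the committee.
2. *Criteria.* SAP 6.6.3.5 gives none. The protocol shows that objective ones exist. Protocol 2.3.1.1 describes the Phase 2 approach: "Adjusting the event rate to censor values that failed quality control criteria designed to rule out non-reproducible and factitious hyperkalemia", with raised lactate dehydrogenase and non-reproduction in a second sample as examples. Protocol 8.4.7.1 calls for a repeat value within 48 hours when the investigator suspects a spurious result. The SAP adopts neither as an adjudication rule.
3. *Direction.* The Phase 2 adjustment worked by removing values. Together with the one-sided selection, this makes a downward adjustment the likely one. That is an inference; the SAP does not state it.
4. *Reach.* The 6.6.3.4 tables are planned in their own right. Laboratory summaries and shift tables (6.6.3.2), adverse events of special interest reported on the eCRF (6.6.2.3) and the primary systolic pressure analysis (6.4.1.4) are not built from the adjudicated listing.

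**Sensitivity of the adjusted table**

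Inputs: about 60 subjects randomised 1:1 (SAP 2.2), each planned to receive both treatments (SAP 5.2). The denominator is therefore about 60 per treatment in total, and about 60/2 = 30 per treatment within a period.

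- One subject, treatment total: 1/60 = 1.7 points.
- One subject, within a period: 1/30 = 3.3 points.

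The public documents give no event counts for this trial, so the counts below are assumptions. Nine of 60 (15.0%) was chosen only for scale: Protocol 4.5 reports potassium above 5.0 mmol/L in 14.9% of lorundrostat subjects in the Phase 1 study. With a and b subjects counted on lorundrostat and placebo, and r and s removed:

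difference = (a − r)/60 − (b − s)/60; ratio = (a − r)/(b − s)

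| Raw counts | Removed (drug, placebo) | Adjusted incidence | Difference (points) | Ratio |
|---|---|---|---|---|
| 9 v 3 | 0, 0 | 15.0% v 5.0% | 10.0 | 3.00 |
| 9 v 3 | 1, 0 | 13.3% v 5.0% | 8.3 | 2.67 |
| 9 v 3 | 2, 0 | 11.7% v 5.0% | 6.7 | 2.33 |
| 9 v 3 | 3, 0 | 10.0% v 5.0% | 5.0 | 2.00 |
| 9 v 3 | 3, 1 | 10.0% v 3.3% | 6.7 | 3.00 |
| 9 v 6 | 0, 0 | 15.0% v 10.0% | 5.0 | 1.50 |
| 9 v 6 | 3, 0 | 10.0% v 10.0% | 0.0 | 1.00 |
| 15 v 6 | 0, 0 | 25.0% v 10.0% | 15.0 | 2.50 |
| 15 v 6 | 3, 0 | 20.0% v 10.0% | 10.0 | 2.00 |

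Drug-only removal is the extreme case. Removing the same third from both treatments (9 v 3, removing 3 and 1) leaves the ratio at 3.00. The hazard is therefore differential removal, which is what masking guards against.

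**The case against.** The best defence has four parts.

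*The charter may mask the committee.* It is not available, and the SAP wording is awkward: it may describe the state of the database and the choice of subjects rather than what adjudicators are shown. This stands as a caution against asserting that they will see treatment codes. It does not remove the point, because a charter that masks the committee would sit badly with an SAP that specifies unblinded data. The SAP text needs correcting either way.

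*The adjusted tables are additional, and changes can be traced.* This stands. The unadjudicated tables remain, each decision needs a documented rationale, and the shared layout makes comparison easy. A reader might infer that the potassium evidence as a whole is unprotected from bias; the documents do not support that. But the SAP does not say which set is the main result, and traceability exposes differential decisions rather than preventing them.

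*Events are not necessarily moved between treatments.* A reader might take the committee's review of event assignment to mean that it can reattribute an event from lorundrostat to placebo or back. The phrase is ambiguous and could equally mean the outlier level in Table 10. SAP 6.6.1 already allocates safety events to treatment by a fixed rule that covers the washout. Reattribution is therefore not established.

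*Spurious values are real and can be checked objectively.* This also stands, and is a reason to write the checks into the SAP. Protocol 4.5 says of the Phase 2 potassium elevations: "One of the events was assessed as erroneous due to sample misprocessing". A reader might infer that one in six high values was false. The text reports six subjects above 6.0 mmol/L and one erroneous event; it gives no number of values, and it says nothing about judgement with treatment known.

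**Conclusion.** The point holds within limits. SAP 6.6.3.5 bases a judgement on unblinded data, states neither masking nor criteria, and carries the outcome into by-treatment safety tables. Treatment-aware decisions could differentially reduce events there. Each reclassified subject is worth about 1.7 points in a treatment total, and about 3.3 points in a within-period column. Two or three one-sided decisions could change the impression the adjusted table gives.

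This assumes about 60 subjects exposed to each treatment. The differences in the table also rest on assumed counts and, in the largest shifts, on removals from lorundrostat alone; they show sensitivity and do not predict bias. Nothing in the documents shows that such decisions were or will be made. The effect is confined to the adjusted tables, so this is a worthwhile correction to a supplementary safety display and no threat to the primary result.

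**What to change.** Amend SAP 6.6.3.5 and align the charter:

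- Adjudicators work before unblinding or, if that has passed, from a listing masked to treatment, sequence and period.
- They rule only on whether the laboratory value is valid, using criteria fixed before unblinding, for example sample-quality markers and the repeat sample.
- Allocation of events to treatment follows the programmed rule in SAP 6.6.1 and is not adjudicated.
- The unadjudicated tables of 6.6.3.4 are labelled the main result and the adjudicated tables supportive.
- The number of subjects reclassified is reported by treatment.

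The cost is SAP and charter wording, a masked listing and at most a short delay before unblinding. No new data are needed. The change should be made before the committee sits, since masking cannot be restored for adjudicators who have already seen the codes.
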